
2. Objectives (include all primary and secondary objectives)

Primary objectives:

- 1) To determine to what extent pathological abnormalities (i.e., MT measures of demyelination, and DTI measures of axonal integrity) are associated with sensory and motor impairments and locomotor patterns (i.e., kinematic walking measures and quantitative motor impairments) in women with AMN.
- 2) To determine the extent to which tract specific anatomy (demyelination, axonal loss) predict who will respond best to three months of progressive resistance training (PRT) in female carriers.

Date: July 1, 2013
Principal Investigator: [name]
Application Number: NA_00045673

3. Background (briefly describe pre-clinical and clinical data, current experience with procedures, drug or device, and any other relevant information to justify the research)

Adrenomyeloneuropathy (AMN) is the adult phenotype of X-linked adrenoleukodystrophy (X-ALD), a progressive disorder that affects the nervous system, adrenal cortex and testes due to a defect in the gene ABCD1, which has been mapped to Xq28. Adult onset of symptoms of disease not only occurs in 60% of males with the X-ALD mutation in their most productive years of life but also 50% of female carriers, though often a decade later than that of the men. Diagnosis and treatment studies for AMN have principally focused on men despite the prevalence of symptoms in female carriers. AMN is characterized by progressive non-inflammatory axonopathy in the corticospinal (CST) and Dorsal Column-Medial Lemniscal (DC-ML) tracts of the brain and spinal cord. There is additional evidence of demyelination caused by secondary inflammatory mechanisms. AMN including women carriers have been characterized as having primarily lower extremity spasticity, with abnormalities in vibration sensation, strength, walking, and balance that progress during 5 to 20 years in a variable pattern. Our preliminary data show that women carriers can have symptoms that are as severe as the men. There are currently no medical treatment options available for women carriers; these patients have dismal hopes for improvement, except with rehabilitation. There is a glaring need for more knowledge and more effective rehabilitative treatment approaches for women ALD carriers.

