We will examine subjects at the level of functional disability (i.e. clinical rating scales), at the level of impairment (i.e., strength and sensation), and at the level of anatomy (i.e., MTI and DTI). The general paradigm includes four parts, requiring 1.5-3.5 hours for testing, depending on the number of activities done. Part 1 is the clinical neurological evaluation which includes clinical rating scales along with measures of lower extremity impairments and quality of life, requiring one hour. Part 2 is the laboratory testing of global walking requiring 30 minutes. Part 3 is evaluation and instruction for a custom exercise program, requiring one hour. Part 4 involves conventional imaging and measures of DTI and MTI in the brain and spinal cord to be completed in the F.M. Kirby Center in KKI, across the hall from the Motion Analysis

Date: July 1, 2013
Principal Investigator: [name]
Application Number: NA_00045673

Laboratory (requiring one hour). We will allow rest breaks as needed by each individual. Parts 1, 2, and 3 will be conducted at the Motion Analysis Laboratory located in KKI. All subjects will participate in 3 testing visits, one at baseline, one at 12 weeks and one at 18 weeks from the baseline visit. All subjects will be asked to participate in parts 1-4 at the baseline visit, and only parts 1 and 2 during visits 2 and 3.

Thus, for testing the breakdown for the time is as follows:

Baseline visit: 1 hr. clinical exam, 30 min. gait test, 1 hr. exercise instruction, 1 hr. MRI scan

12th week visit: 1 hr. clinical exam, 30 min. gait test

18th week visit: 1 hr. clinical exam, 30 min. gait test

All subjects will undergo a functional sensorimotor assessment at every testing session with the purpose of systematically documenting clinical status. The primary investigator or physical therapist and research coordinator will conduct this exam. The exam will include standard clinical measures of sensation (vibration, proprioception), strength, tone (Modified Ashworth), and passive range of motion. In addition, we will use standardized quantitative scales to evaluate walking, ataxia, and overall disease impairment in these individuals. Lastly, self report measures of quality of life and pain will be used.

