Healthy controls have the same exclusion criteria as women with AMN with 2 exceptions, (1) they can be age 21-70 years, and (2) they will not be carriers for X-ALD. They must have normal neurological function.

6. Drugs/ Substances/ Devices

- a. The rationale for choosing the drug and dose or for choosing the device to be used.

N/A

- b. Justification and safety information if FDA approved drugs will be administered for non-FDA approved indications or if doses or routes of administration or participant populations are changed.

N/A

- c. Justification and safety information if non-FDA approved drugs without an IND will be administered.

N/A

Study Statistics

- a. Primary outcome variable.

Primary outcome variables for sensorimotor impairments include: vibration sensation, strength (average values from the hip and ankle muscles, both flexion and extension, will be used), and spasticity from the ankle flexor/extensor muscles bilaterally.

The primary variables of interest for white matter integrity in this analysis will be fractional anisotropy (FA) and magnetization transfer ratio (MTR).

Other primary outcome variables include correlations to determine relationships between sensorimotor impairments and between white matter integrity variables in the tracts of interest. Multiple regression analysis we will also be used determine to what extent sensorimotor impairments are related to white matter integrity variables.

The primary outcome variable for the exercise intervention we will calculate a functional composite score (FS) for each person that will incorporate 4 tests that functionally challenge the lower extremity: 1) sit to stand, 2) Up and Go test, 3) 25-foot timed walk, and 4) 6-minute walk test.

- b. Secondary outcome variables.

To determine response to three months of the exercise intervention:

1. We will calculate pre- to post- trial differences between groups using an unpaired t test. Changes between pre- and post-trial within groups will also be compared with paired t tests.

Date: July 1, 2013
Principal Investigator: [name]
Application Number: NA_00045673

2. To determine change in hip flexion, FS from post- to follow up session within groups will be compared with paired t tests. [(Exercise_{followup}-Exercise_{post}) vs (Exercise_{post}-Exercise_{pre})], will be evaluated.

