 3. To evaluate possible time and group interactions during the intervention within groups we will use multivariate ANOVA's. Significant interactions will be evaluated with a mixed effects linear regression.
 4. To determine change in EDSS scores over each session we will use with Wilcoxon signed rank test.
 5. To determine whether specific changes in the primary outcome measures are predicted by the changes in tract specific demyelination and axonal loss (i.e., MTR and FA) we will determine how much each impairment changed from the pre- to post- session.
 6. We will conduct separate correlations to determine the relationship between the primary outcomes, and extent of demyelination and axonal loss pre- and post-intervention.
 7. Multiple regression analyses will also be used to determine which pattern of white matter damage (i.e., demyelination, axonal loss) best predicts hip flexion and FS.
- c. Statistical plan including sample size justification and interim data analysis.

Preliminary studies of heterozygote data from our laboratory suggest that a minimum of 12 subjects are needed to obtain adequate statistical power. Hip flexion strength data from female carriers are: 11.2 ± 4.6 kg. Using these values, differences between groups on the order of one SD will be statistically significant with a power of 0.8 given a sample size of 12 subjects. To account for attrition, we have added 25% to this total. Therefore, our initial plan is to have 15 female carriers for this project and 15 healthy controls. All power calculations assume two-tailed tests with $\alpha = 0.05$. Analysis will be done using Statistica software (StatSoft Inc., Tulsa OK) or Stata (StataCorp).

- d. Early stopping rules.

None.

7. Risks

- a. Medical risks, listing all procedures, their major and minor risks and expected frequency.

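### Item 7, the only regression linking imaging to the training outcomes, is not anchored to baseline, so read literally it can report a marker of severity as a marker of response

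*Combined protocol and SAP*

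**What the plan says.** All places are in the combined protocol and SAP.

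- **Section 2, primary objective 2:** tract-specific anatomy is to "predict who will respond best to three months of progressive resistance training (PRT) in female carriers".
- **Study Statistics, b, list heading:** "To determine response to three months of the exercise intervention".
- **Item 2 of that list:** "To determine change in hip flexion, FS from post- to follow up session". This is the same outcome pair as in item 7, explicitly as change.
- **Item 5:** asks whether changes in the primary outcomes are "predicted by the changes in tract specific demyelination and axonal loss (i.e., MTR and FA"), using pre- to post-session change in each impairment.
- **Item 6:** "separate correlations to determine the relationship between the primary outcomes, and extent of demyelination and axonal loss pre- and post-intervention".
- **Item 7:** multiple regression to "determine which pattern of white matter damage (i.e., demyelination, axonal loss) best predicts hip flexion and FS".
- **Section 4a:** imaging is part 4 of the testing. All four parts are done at baseline, and "only parts 1 and 2 during visits 2 and 3".
- **Study Statistics, a:** FA and MTR are the imaging variables. A separate regression asks "to what extent sensorimotor impairments are related to white matter integrity variables", which is objective 1. FS is a composite of four functional tests computed for each person; it is not defined as a change.

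**The concern.** Response is a change from where a woman started. Item 7 names outcomes that exist at baseline, week 12 and week 18, and does not say which visit is used or whether the starting value is taken into account.

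Hypothesis 1 in the Abstract expects the imaging measures to track weakness and disability. If it is right, women with better tract measures start stronger and, other things equal, finish stronger. A regression of the week 12 level on imaging would then largely re-test objective 1 while being reported as an answer to objective 2.

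Nothing else in the list fills the gap. Item 3's mixed model has no imaging predictor, item 6 is correlations, and item 5 depends on follow-up imaging that is not scheduled. Followed to the letter, the plan has no runnable change-based regression for one of its two primary objectives. The Abstract and section 8 say that the findings should help clinicians predict who is likely to respond, so mistaking severity for response would matter.

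**Working it through.** **The plan's own figure.** None is given for item 7. The only power statement (Study Statistics, c) is 0.8 for a one-SD difference between groups with 12 subjects. That is a different comparison and does not bear on this point. The enrolment figure does follow: 12 × 1.25 = 15 carriers.

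**Inputs from the documents.** n = 12 to 15 carriers; two-sided α = 0.05; hip flexion 11.2 ± 4.6 kg (Study Statistics, c). One entry route is hip flexion of 6.6-15.8 kg (section 5), which is 11.2 − 4.6 to 11.2 + 4.6, or ±1 SD.

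**Inputs assumed, because the documents give none.** Marker-baseline correlation r from 0 to 0.7; baseline-week 12 correlation ρ of 0.8-0.9; or, in the second model, measurement reliability k of 0.8-0.9.

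**Null hypothesis in every case.** The marker carries no information about response.

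*Model A, gain falls with baseline.* Marker M = rB + √(1−r²)e; week 12 value Y = ρB + √(1−ρ²)u; e and u independent.

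- Level: corr(M, Y) = rρ, from 0.3 × 0.8 = 0.24 to 0.7 × 0.9 = 0.63.
- Baseline-adjusted: partial correlation 0, so 5%.
- Change: correlation −r√((1−ρ)/2), at most 0.7 × √0.1 = 0.221 in size.

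*Model B, constant gain, baseline and week 12 both measured with error.* M correlates r with the true value.

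- Level: corr(M, Y) = r√k, up to 0.7 × √0.9 = 0.664.
- Change: correlation 0, so 5%.
- Baseline-adjusted: partial correlation r√k(1−k)/√((1−r²k)(1−k²)). At r = 0.7, k = 0.8 this is 0.1252/√(0.608 × 0.36) = 0.268.

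**From correlation c to false-flag rate.** Approximately P(Z > 1.96 − √(n−3)·atanh c) plus the small opposite tail, with n−4 in place of n−3 for the adjusted model.

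- c = 0.24, n = 12: 11.4% (simulation about 12%).
- c = 0.63, n = 15: 72.9% (simulation 76%).
- c = 0.664, n = 15: 79.1% (simulation 82%).
- Change, 0.221, n = 15: 12.2% (simulation 12%).
- Adjusted, 0.268, n = 15: 14.9% (simulation 15%).

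**Entry range.** A normal variable cut at ±1 SD has SD √(1 − 0.709) = 0.540. With ρ = 0.9 and r = 0.7 before truncation, the marker-baseline correlation falls to 0.7 × 0.540/√(0.49 × 0.291 + 0.51) = 0.468 and the baseline-week 12 correlation to 0.744. Their product is 0.348, which gives 24.2% at n = 15 (simulation 25%). At r = 0.3 the product is 0.167 × 0.744 = 0.124, which gives 7.2%.

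**Results, single marker, simulation with 20,000 trials per setting, n = 12 and 15:**

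| Setting | Week 12 level | Baseline-adjusted | Change |
|---|---|---|---|
| r = 0 | 5% | 5% | 5% |
| r = 0.3, models A and B | 12-18% | 5-6% | 5-6% |
| r = 0.5-0.7, model A | 26-76% | 5% | 6-12% |
| r = 0.5-0.7, model B | 32-82% | 6-15% | 5% |
| Hip flexion, all enter through 6.6-15.8 kg, r = 0.3 | 6-7% | 5% | 5% |
| Same, r = 0.5-0.7 | 8-25% | 5% | 5-6% |

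The last two rows use model A. FS is not directly truncated by the entry range. Women admitted on hip extension would put hip flexion between the truncated and untruncated rates.

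**The case against.** The strongest reply is that a level model is the less natural reading. The list heading speaks of response, item 2 uses the same two outcomes for change, item 5 computes pre- to post-session change, and section 8 says the study will evaluate how far myelin and axon integrity predict the best responders. This stands. A reader might infer that the plan commits to a level model; the documents do not support that. They leave the outcome undefined, and the wording admits a baseline or week 18 level as readily as a week 12 level.

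Item 6 should not be pressed as evidence for a level reading either. Its reference to pre- and post-intervention may attach to the imaging, in which case it has the same missing-scan problem as item 5.

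The second reply is that the size rests on assumed correlations. This also stands. The Abstract says that the relation between damage and disability in these women is unknown, and that past attempts at such correlations had limited success (it blames rating scales and routine imaging). At a weak correlation, with the hip flexion entry range in force, the error is close to nominal.

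Neither reply removes the gap: a heading does not define an outcome variable, and item 5 cannot supply one.

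**Conclusion.** The point holds as under-specification of the one regression that can serve primary objective 2, together with an item 5 that cannot be run as written. Under the assumed correlations, a week 12 level model would falsely flag a single marker in about 12-18% of trials at r = 0.3 and 26-82% at r = 0.5-0.7. The corresponding rates are 5-15% with baseline adjustment (about 5% if baseline is error-free) and 5-12% for change. For hip flexion under the entry range the level rate is about 6-7% at r = 0.3 and 8-25% at r = 0.5-0.7.

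Two stronger readings should be resisted. A reader might take the upper percentages as this trial's expected error rate; they apply only if a level model is fitted and imaging tracks severity strongly, and the documents establish neither. A reader might also infer that the result will decide who is offered rehabilitation; the documents speak only of helping clinicians predict likely responders.

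This should be corrected, because a primary objective rests on it and the data needed are already collected.

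**What to change.** Rewrite item 7 as follows: in carriers, baseline FA and baseline MTR in prespecified tracts predict week 12 FS, and separately week 12 hip flexion, with the baseline value of the same outcome as covariate. Report the model for week 12 minus baseline change as a sensitivity analysis. Both are worth showing because adjustment is slightly biased when baseline is noisy, and change is slightly biased when gain falls with baseline.

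Restate item 5 to use baseline MTR and FA, since changes in them are not measured.

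Label the result exploratory. State that, because all subjects train, the model predicts change during training and cannot separate it from other change over time.

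The cost is SAP wording, one degree of freedom and one extra model; no new data or visits. Power stays low: for one marker with partial correlation 0.5 given an error-free baseline, the adjusted model has 36-47%. A non-significant marker should therefore not be reported as ruled out. Requiring both models to agree, or allowing only one tract summary per marker, would reduce false claims at the expense of power or of tract detail. Those are trade-offs for the study team, not part of this correction.

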Date: July 1, 2013
Principal Investigator: [name]
Application Number: NA_00045673

Johns Hopkins Medicine - eForm A

1. Abstract

- a. Provide no more than a one page research abstract briefly stating the problem, the research hypothesis, and the importance of the research.

X-linked adrenoleukodystrophy (X-ALD), a progressive neurodegenerative disease, is caused by a defect in the ABCD1 gene. The disease has multiple phenotypes, but the most common adult form is adrenomyeloneuropathy (AMN), which presents as a slowly progressing spastic paraparesis with sensory and autonomic dysfunction. In a previous study we linked corticospinal tract (CST) and Dorsal Column (DC) abnormalities to lower extremity sensory loss and weakness in men with AMN; however, there have been no studies evaluating these relationships in woman heterozygote carriers (i.e., women with AMN). It is unknown, in women with AMN, how the pattern of damage in the brain and spinal cord relates to disability and if these patterns predict responsiveness to treatment. While conventional magnetic resonance imaging (MRI) techniques have been used to evaluate progression of X-ALD disease burden, attempts at correlating clinical disability with axonal injury have had limited success due to clinical rating scales that do not adequately measure all aspects of the disease, coupled with an inability for routine imaging techniques to quantify relevant fiber tracts in the brain and spinal cord. We propose to comprehensively evaluate the CST and DC across the brain and cervical spinal cord with the purpose of understanding mechanisms of disability in women with AMN. We hypothesize that: 1) tract-specific magnetization transfer imaging (MTI) and diffusion tensor imaging (DTI) will predict specific sensory and motor impairments (i.e., sensory loss and weakness) and disability; and 2) tract-specific MTI and DTI will predict who is likely to respond best to progressive resistive training (PRT). For this project we are using a rigorous biologic approach that combines clinical evaluation, neuroimaging, and measures of impairment and disability to provide a more precise prognosis in terms of physical disability and to predict who is likely to respond to a physical intervention. We predict that many of the women will improve their strength and function following the PRT program. Specifically, we predict that axonal loss will be associated with irreversible disability. By contrast, demyelination may have potentially reversible injuries that would benefit from PRT in improving disability. The linking of this information will not only be important for better defining disability in women heterozygote carriers of AMN but it will also help to guide physicians and rehabilitation therapists in predicting who is likely to respond to rehabilitative interventions, as well as for optimizing outcomes for future neuroprotective pharmacological interventions.

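### Item 7's regression leaves the imaging predictors, tract and level open in about 12–15 carriers, with no check outside the fitted data, so its fit cannot support claims about predicting responders

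*Combined protocol and SAP*

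**What the plan says.** Study Statistics b (Secondary outcome variables), item 7, plans multiple regression to establish "which pattern of white matter damage (i.e., demyelination, axonal loss) best predicts hip flexion and FS". FS, the functional composite score, is named in Study Statistics a as the primary outcome variable for the exercise intervention.

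The possible predictors have to be pieced together. Study Statistics a names FA and MTR as the white-matter measures of main interest and speaks of "white matter integrity variables in the tracts of interest", in the plural. The Abstract says the project will "comprehensively evaluate the CST and DC across the brain and cervical spinal cord".

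On size, Study Statistics c states that "a minimum of 12 subjects are needed to obtain adequate statistical power" and that "our initial plan is to have 15 female carriers for this project and 15 healthy controls". That calculation concerns a between-group difference in hip flexion strength and does not cover the regression.

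The documents give no predictor list, entry or selection rule, criterion for the best pattern, validation step or multiplicity control for item 7. They also do not say which participants enter the model.

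**The concern.** Primary objective 2 (section 2) is to establish how far tract-specific anatomy predicts which carriers respond best to the training programme. Item 7 sits under secondary outcomes, but it is the listed analysis closest to that objective. The Abstract and section 8a expect the results to help physicians and therapists predict who is likely to respond. That is a statement about women who were not in the sample.

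With so few women, fit measured on the data used to build the model can be high by chance in two ways. Raw R² rises with each predictor added, whether or not it carries information. And if the tract and level are picked because they fit best, the nominal p-value of the chosen model ignores the search. The plan excludes neither. A chance pattern could then be reported as the type of white-matter damage that identifies responders.

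**Working it through.** **Inputs**
- Metrics: 2, FA and MTR (Study Statistics a).
- Tracts: 2, CST and DC; regions: 2, brain and cervical cord (Abstract).
- Candidates: 2 × 2 × 2 = 8. This is derived and not stated. The range used is 2 (one FA, one MTR) to 8; separate left and right measures or further DTI measures would raise it.
- n: 12 (minimum) and 15 (planned carriers); 30 if controls were pooled.
- Outcomes in item 7: 2, hip flexion and FS.

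**The plan's own figure.** There is none for this regression. The step from 12 to 15 reproduces as 12 × 1.25 = 15. The power claim behind the 12 (0.8 for a one-SD difference between groups) is a separate matter, and nothing below depends on it.

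**Step 1: raw R² when imaging is uninformative.** With k pre-specified null predictors and normal errors, R² follows Beta(k/2, (n−k−1)/2), so E[R²] = k/(n−1).

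| k | n=12 | n=15 |
|---|---|---|
| 2 | 2/11 = 0.18 | 2/14 = 0.14 |
| 4 | 4/11 = 0.36 | 4/14 = 0.29 |
| 8 | 8/11 = 0.73 | 8/14 = 0.57 |

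With eight predictors the residual degrees of freedom are 12−8−1 = 3 and 15−8−1 = 6. The chance of a null R² of at least 0.5 is 0.88 (n=12) and 0.66 (n=15). With two predictors it is 0.04 and 0.02. Pooling controls gives 8/29 = 0.28.

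**Step 2: the overall F test of a pre-specified model.** Type I error is 5% whatever k is. With eight predictors, significance needs R² of at least 0.96 (n=12) or 0.85 (n=15), so the expected null values of 0.73 and 0.57 would not be significant. With two predictors the thresholds are 0.49 and 0.39.

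**Step 3: a two-term model chosen from the data.** Null datasets were simulated with eight predictors at assumed pairwise correlations of 0, 0.5 and 0.8. The best-fitting pair was kept and tested as if it had been fixed in advance.

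| How the pair is chosen | Pairs searched | Nominal p<0.05 (n=12 and 15) |
|---|---|---|
| FA and MTR from the same location | 4 | about 15–19% |
| Best FA plus best MTR | 4 × 4 = 16 | about 29–34% |
| Any two of eight | 8 × 7/2 = 28 | about 36–42% |

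Median null R² is 0.40–0.41 (n=12) or 0.31–0.32 (n=15) for best FA plus best MTR, and 0.44–0.45 or 0.35 for any two of eight. These ranges cover all three correlations, so correlation among the tract measures does not remove the inflation. These rates are for one outcome, and item 7 has two.

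**Step 4: would an out-of-sample measure reveal this?** Yes. For the eight-predictor null model, median leave-one-out R² is about −5.9 (n=12) and −2.1 (n=15), against in-sample averages of 0.73 and 0.57.

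**The case against.** The strongest reply is that item 7 names two patterns, demyelination and axonal loss, and Study Statistics a names two measures. One MTR term and one FA term is therefore a natural reading. Fixed in advance, such a model has an expected null R² of only 0.14–0.18, and its F test holds 5%. The tracts and regions come from a scope sentence in the Abstract and not from the statistical section. A reader might infer that the plan sets out an eight-predictor model; it does not, and eight is only the number of candidates its wording allows.

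A reader might also infer that the regression is bound to look predictive. That too goes further than the text. It holds for raw R² from a large model and for undeclared selection, but not for a pre-specified model judged by its F test. The plan commits to none of these. Nor does every two-term choice carry the same optimism: one FA and one MTR from a common location is inflated to about 15–19%, well below the rate for any two of eight.

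The population is open as well. Item 7 does not name it, and section 4a has all subjects, controls included, scanned at baseline. Pooling to n=30 would lower the eight-predictor null R² to 0.28, but primary objective 2 is about carriers.

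Finally, leave-one-out R² is itself imprecise at 12–15 women, and the wording about guiding clinicians describes a hoped-for benefit, not a decision rule.

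All of this limits how strongly the point can be put. It does not remove it: no section says which tract and level would supply the two terms, and if the data decide, the error rate exceeds 5% in every version examined.

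**Conclusion.** The point stands in conditional form. The predictors, tract, level and criterion for the best pattern are unspecified, and no planned analysis tests prediction in women outside the fitted data. Depending on how the gap is filled, expected raw R² with uninformative imaging runs from 0.14 (two fixed predictors, n=15) to 0.73 (eight, n=12). The nominal 5% error rate of a two-term model runs from 5% (fixed in advance) to about 42% (any two of eight).

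This rests on the derived count of eight, a carriers-only model with 12–15 women, normal errors and the assumed correlations. The documents do not show that a misleading result will follow. They show that nothing in the plan prevents one, in the analysis closest to a primary objective. The change should be made before the imaging data are related to outcome.

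**What to change.** 1. Before analysis, state that the main model uses carriers, and name one FA and one MTR measure, each with its tract and level. Use no data-driven selection.
2. Report leave-one-out R² or prediction error against a model without imaging, defined as an intercept plus the baseline value of the outcome. The imaging model should carry the same baseline term. Acknowledge how imprecise the estimate is at this sample size.
3. Base any statement about predicting responders on that comparison and not on in-sample R².
4. Report the other tract and level models, including CST against DC, as exploratory, and repeat any selection step inside each cross-validation fold.

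The cost is analysis-plan wording and a little computation, with no extra participants, scans or visits. There are two real downsides. The tract comparison becomes exploratory although objective 2 refers to tract-specific anatomy, so the choice of the named tract and level needs a stated rationale. And the reported fit will be less impressive. Power stays limited too: for two fixed imaging predictors with a true R² of 0.5, the F test has power of about 0.67 (n=12) or 0.79 (n=15), before any baseline term is added. Eight predictors with the same total true R² give about 0.16 or 0.32.

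### The claim that 12 subjects give adequate power rests on a group difference in hip flexion strength, which is neither primary objective; both are correlation or regression questions in carriers, for which no power or precision is stated.

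*Combined protocol and SAP*

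**What the plan says.** Section 2 sets two primary objectives. The first is "To determine to what extent pathological abnormalities (i.e., MT measures of demyelination, and DTI measures of axonal integrity) are associated with sensory and motor impairments"; gait measures are covered as well, and the population is women with AMN. The second is "To determine the extent to which tract specific anatomy (demyelination, axonal loss) predict who will respond best"; here the response is to the 12-week training programme, and the population is female carriers.

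Study Statistics, part a names the primary impairment variables: vibration sensation, strength averaged over hip and ankle muscles, and ankle spasticity. The imaging variables are FA and MTR, and the methods are correlation and multiple regression. The primary outcome for the exercise intervention is FS, a composite of four lower-extremity tests.

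Part b (secondary) lists unpaired t tests between groups on pre-to-post differences (item 1). It also lists regressions of hip flexion and FS on the pattern of white matter damage (item 7).

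Part c opens with "Preliminary studies of heterozygote data from our laboratory suggest that a minimum of 12 subjects are needed to obtain adequate statistical power". It cites hip flexion strength of 11.2 ± 4.6 kg in carriers. The effect considered is "differences between groups on the order of one SD", and the plan says that an effect of this size "will be statistically significant with a power of 0.8 given a sample size of 12 subjects". It adds 25% for attrition, which gives 15 carriers and 15 controls, and states that "All power calculations assume two-tailed tests" at 0.05. There is no other power or precision statement.

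**The concern.** The adequacy statement is unqualified, but the calculation belongs to a different question. A difference in mean strength between carriers and controls says nothing about how precisely 12 or 15 carriers can estimate a correlation between FA or MTR and impairment, or a regression of training response on imaging. Hip flexion alone is not the primary outcome for either objective: the first uses strength averaged over hip and ankle muscles, and the exercise outcome is FS.

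The risk lies in interpretation. A non-significant correlation would be reported beside a stated power of 0.8 that does not apply to it, and could be taken as evidence that imaging is unrelated to function or does not predict response. Section 8 expects the results to help clinicians and therapists predict who will respond, so a false negative reading has consequences. Both objectives also ask about extent, which is an estimation question that the power sentence does not address.

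**Working it through.** **Inputs from the plan.** Two-sided α = 0.05, power 0.8, effect one SD (4.6 kg), n = 12, enrolment 15 + 15 (Study Statistics, part c). The 15 + 15 enrolment implies 12 per group.

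**Inputs not in the plan.** No expected r, R-squared or number of predictors is given, so I solve for the detectable value. I take n = 15 for objective 1, because MRI and impairment testing are both done at baseline (section 4a). I take n = 12 for objective 2, assuming the planned attrition occurs.

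**1. The plan's own figure.** For two groups of n and d = 1, the noncentrality is d√(n/2).
- Normal approximation, n = 12: √6 − 1.960 = 2.449 − 1.960 = 0.489, so power is 68.8%.
- Noncentral t, 22 df: 64.9% at 12 per group and 75.3% at 15 per group.
- For 80%: 2(1.960 + 0.842)² = 15.7, so 16 per group by the normal approximation; the t test needs 17.
- If 12 were the total (6 per group), power would be 34.7%.
- A one-sided normal calculation gives 78.9%, but the plan says two-tailed. A one-sample or paired test with n = 12 gives 88.3%, but the plan says between groups.

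The stated 0.8 is not reproduced. The attrition step is: 12 × 1.25 = 15.

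**2. One correlation, two-sided 0.05.** Under bivariate normality, given U, the t statistic is noncentral t on n − 2 df with noncentrality ρ√U/√(1 − ρ²). U is chi-square on n − 1 df, and power is averaged over U.

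| True r | Power, n = 12 | Power, n = 15 |
|---|---|---|
| 0.3 | 15% | 19% |
| 0.4 | 26% | 32% |
| 0.5 | 40% | 50% |
| 0.6 | 58% | 70% |
| r for 80% power | 0.712 | 0.652 |

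Rounded up so that power is at least 80%, these are 0.72 and 0.66. The Fisher z approximation, tanh[(1.960 + 0.842)/√(n − 3)], gives 0.73 and 0.67.

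**3. Two predictors (FA and MTR).** Using noncentral F with noncentrality nR²/(1 − R²), 80% power needs R-squared of 0.53 (n = 12) or 0.45 (n = 15). This treats the predictors as fixed. Averaging over random predictors as in step 2 (n replaced by U) raises these to 0.59 and 0.50.

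**4. Multiplicity, as an illustration.** Three impairments by two imaging measures in one tract is six tests. At α = 0.05/6, the method of step 2 gives |r| of about 0.81 (n = 12) and 0.76 (n = 15).

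**5. Precision.** The Fisher z interval is tanh[atanh(r) ± 1.96/√(n − 3)].
- Observed r = 0: tanh(1.96/√12) = 0.51 at n = 15 and tanh(1.96/3) = 0.57 at n = 12, so the intervals are ±0.51 and ±0.57.
- Observed r = 0.5: −0.02 to 0.81 (n = 15) and −0.10 to 0.83 (n = 12).

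**6. Smallest significant r.** t/√(n − 2 + t²) gives 2.160/√(13 + 4.667) = 0.51 (n = 15) and 2.228/√(10 + 4.965) = 0.58 (n = 12).

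**The case against.** **The power sentence does attach to something planned.** Part b lists between-group t tests, and hip flexion is a regression outcome beside FS in item 7. That stands, but both appear under secondary outcomes, and in item 7 hip flexion is predicted by regression, not compared between groups.

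**Controls are scanned too and might be pooled.** The statistics section does not name the analysis set for the correlations. Pooling would lower the Fisher z threshold to about 0.55 (n = 24) or 0.49 (n = 30). Both objectives are worded for carriers, however, and a pooled correlation would partly reflect the carrier-control difference.

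**The detectable values are themselves simplified.** This stands. They hold for one unadjusted Pearson test, and they do not carry over to spasticity if it is scored on the ordinal Modified Ashworth scale listed in section 4a. Any replacement text must say so, or it becomes a second misplaced power claim.

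**Stronger readings that the documents do not support.**
- A reader might infer that 15 carriers are too few. No expected r is given, so a true association of 0.65 to 0.72 cannot be called implausible.
- A reader might infer that any significant correlation will be inflated. That depends on the true r. In simulation at n = 15, the mean significant r is 0.65 when the truth is 0.5, but 0.73 when it is 0.71 and 0.80 when it is 0.80.
- A reader might convert the one-SD group difference into a correlation and quote its power. That correlation is between group and strength in a pooled sample, and has no link to an imaging-impairment correlation within carriers.

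**Conclusion.** The concern holds in limited form. The adequacy claim is not supported for either primary objective, and its 0.8 is not met for the comparison that it describes (about 65% at 12 per group). For the primary analyses the sample gives 80% power only for strong associations: |r| of about 0.66 (n = 15) or 0.72 (n = 12), or R-squared of at least about 0.45 or 0.53 with two predictors. These figures assume carriers-only analyses, bivariate normality, one test at 0.05 and 12 completers for objective 2. Multiplicity raises them. Whether such associations are likely cannot be judged from the documents. Significant estimates will tend to be inflated only if the true correlation is modest. The defect is in the justification and the interpretation that it invites, not a demonstrated need for more patients.

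**What to change.** Keep 15 carriers and change the text of Study Statistics, part c.

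1. Limit the existing power sentence to the secondary between-group comparison and correct it: for a one-SD difference, two-tailed 0.05, power is about 65% with 12 per group and 75% with 15 per group. Say whether the SD is for strength level, as the 4.6 kg appears to be, or for the change compared in part b, item 1.
2. Add for the primary objectives:

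> For a single unadjusted Pearson correlation (two-sided 0.05), 15 scanned carriers (objective 1) give 80% power at |r| of about 0.66, and 12 completers (objective 2, assuming the planned attrition) at about 0.72. A two-predictor regression (FA and MTR, treated as fixed) needs R-squared of about 0.45 and 0.53. Testing several impairments, measures and tracts raises these thresholds. The primary analyses are therefore estimation.

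3. State that objective 1 uses all scanned carriers, since it needs no follow-up.
4. Report every primary correlation and R-squared with a 95% confidence interval.
5. State that a non-significant result will be reported as inconclusive, not as absence of association, because even an observed r of 0 has an interval of about ±0.51 (n = 15) or ±0.57 (n = 12). A rule that allows a conclusion of no association only when the interval excludes ±0.5 would not work, since at these sizes it could never be met.

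The cost is wording only, with no extra patients, visits or scans. The price is a less favourable stated figure.
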